### 6.2.4 Adjustments for Covariates

[REDACTED] as recorded per CRF will be used, rather than the values coming from the IRT system.

For continuous variables, baseline values and IVIg dose frequency will be explored in the statistical modeling.

### 6.2.5 Multiple Comparisons/Multiplicity

No adjustments for multiplicity will be made.

## 6.2.6 Subgroups

### 6.2.6.1 Subgroup category for secondary endpoints

For the secondary endpoints derived from mMRC, Grip strength, MMN-RODS© and 9-HPT , descriptive statistics will be presented per subgroup based on the [REDACTED]. The value as entered into the CRF will be used, and not the value from IRT, should these defer.

### 6.2.6.2 Subgroup categories for Demographics

**Table 9 Subgroup categories for Demographics**

Subgroup	Categories
Sex	Male, Female
Age	

• 18 to <65 years

• ≥65 years

Weight	

• <50 kg

• 50 to <75 kg

• 75 to <120 kg

• ≥120 kg

BMI	

• Underweight: <18.5 kg/m^2

• Normal weight: 18.5 to <25 kg/m^2

• Overweight: 25 to <30 kg/m^2

• Obese: ≥30 kg/m^2

Region	

• North America: US, Canada

• Europe: EU/EEA/EFTA/UK

• Asia

• Rest of World

## 6.2.7 Missing, Unused, and Spurious Data

### 6.2.7.1 Adverse events missing dates

AEs will be considered treatment-emergent based on their start date/time.

Imputation of missing/partial AE dates/time will be performed only to identify treatment-emergent AEs. If the AE start date/time is incomplete or missing, the AE will be considered treatment-emergent unless the available part of the AE start or stop date/time provide evidence that the event did not occur following initiation of IMP. The following rules allow for an imputed start and stop date that adheres to this convention:

For partial or missing AE start date/time the following imputation will be applied:

1. If year is not missing and is after the year of first IMP dose:
  - a. If month is missing, then month will be imputed as January.
  - b. If day is missing, then day will be imputed as the first of the month.
2. If year is not missing and is the same as the year of the first IMP dose:
  - a. If month is missing, then impute the month as the month of the first dose date.
  - b. If day is missing, and the month is the same as the month of the first dose date, then impute day as the day of the first dose date.
  - c. If day is missing but month is after the month of first dose date, then impute day as the first day of the month.
3. If year is missing then impute the date of the first IMP administration.
4. If the start date is completely missing, but the AE is either ongoing or the stop date or imputed stop date (in case of partially missing stop date) is after the first dose date then impute the start date as the first dose date.
5. For any cases involving the rules above, if the AE stop date or imputed stop date (in case of partially missing stop date) is before the AE start date, then do not impute the AE start date and assume that the AE is treatment-emergent for the purpose of the analysis. Further, if the AE stop date or imputed AE stop date (in case of partially missing stop date) occurs prior to the first dose date, do not impute the AE start date, and assume that the AE is not treatment-emergent.

For partial or missing AE start time the following imputation will be applied:

1. If date or imputed date is the date of the of the first IMP dose, then the time will be the time of the IMP administration
2. If date or imputed date is different from the date of the of the first IMP dose, then time will be 00 h 00 min.

For partial and missing AE stop date/time the following imputation will be applied:

1. If Day only is missing, incomplete stop dates will be replaced by the last day of the month, if not resulting in a date later than the date of the participant's death or date of study discontinuation. In the latter case, the date of death/date of study discontinuation will be used to impute the incomplete end date.
2. If Day & Month are missing, Day & Month will be replaced by 31DEC, if not resulting in a date later than the date of the participant's death or date of study discontinuation. In the latter case, the date of death/ date of study discontinuation will be used to impute the incomplete end date.
3. In all other cases the incomplete end date will not be imputed.

If time is missing, the time will be imputed to 23:59.

Imputed dates and times will not be listed nor will day of onset or event durations be presented if the required date(s) is imputed.

#### 6.2.7.2 Prior and concomitant medications missing dates

Medications and procedures administered will be classified by period of use as prior, concomitant or both prior and concomitant to IMP therapy. In the event of partial dates, the available date information will be used to categorize the initiation period accordingly. In the event that the classification is ambiguous, including for cases of completely missing dates, the medication will be assumed to be both prior and concomitant unless indicated as prior only due to the given stop date.

The following date imputation rules for partially missing dates reflect the above convention:

1. End date: Missing day will be imputed as the last day of the month, and missing month will be imputed by December, if not resulting in a date later than the date of the participant's death, date of study discontinuation or date of study completion. In the latter case, the date of death/date of study discontinuation/ date of study completion will be used to impute the incomplete end date.
2. Start date: Missing day will be imputed as the first day of the month, and missing month will be imputed by January.
3. If the start date is completely missing, then:
  - a. If the end date is prior to the date of first administration of the IMP, then the medication is considered as prior
  - b. If the end date is prior to the date of last administration of the IMP, then the medication is considered as prior and concomitant
  - c. If the end date is completely missing or after the date of last administration of the IMP, then the medication is considered as prior and concomitant.

### 6.3 Study Population

#### 6.3.1 Participant Disposition

Summary data for the ENR set will be presented overall. The denominator for all percentages will be the total number of enrolled participants. Summary data for the SAF set will be presented for each cohort by treatment group and overall.

A tabulation of participant disposition will be presented by treatment group and overall, for enrolled participants, including:

- Number of screened participants
- Number of participants who entered, discontinued the IVDP (including completed IVDP but did not enter IVMP), and who completed IVDP and entered IVMP

- Number of participants who entered, completed and discontinued the IVMP
- Number of screen failures during the screening period, IDVP and IMVP along with the reasons. Screen failures are defined as participants who consent to participate in the clinical trial but are not subsequently randomized to the DBTP. A participant can be screening failure if the participant did not meet protocol criteria at screening visit, IVM1 or V1 or discontinued the study before randomization
- Number of participants randomized

A tabulation of participant disposition will be presented for each cohort by treatment group and overall, for SAF set, including:

- Number of participants who entered, discontinued the IVDP, and who completed IVDP and entered IVMP
- Number of participants randomized
- Number of participants randomized but not dosed
- Number of participants who completed DBTP, who are ongoing and who early discontinued treatment or DBTP and associated reasons for discontinuation. Among these participants, the number of participants who entered into the subsequent periods (Safety follow period or LTE) or did not enter into the subsequent periods will also be described
- Number of participants entering into safety follow-up period, who completed safety follow-up period and who early discontinued the study and associated reason for discontinuation. Among these participants, the number of participants who completed or not the DBTP will be described
- Number of participants entering into the LTE

The number of participants in each analysis set will be also presented in the SAF set. The number of participants per country and site will also be provided using the SAF and ENR sets.

A summary of periods duration will be presented for each period for the SAF set (screening period, IVDP, IVMP, DBTP and Safety follow-up period). For IVDP, IVMP, DBTP and Safety follow-up period, IVIg frequency will be presented by IVIg frequency stratification factor.

The following by-participant listings will be presented.

- Study completion information, including the reason for premature study withdrawal
- Inclusion/exclusion criteria not met
- Inclusion in study Analysis Sets
- Allocation to treatment and IVIg dose frequency stratification factor

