## 4 ANALYSIS SETS

### 4.1 Analysis Set Definitions

The following data sets will be used for the statistical analysis:

**Enrolled (ENR) Set:** all participants who signed an informed consent to participate to the trial

Note: Having signed an informed consent is defined as having a complete date for consent signature in the database.

**Safety (SAF) Set:** All enrolled participants who were randomized and received at least 1 dose, or part thereof, of IMP (ARGX-117 or placebo). Participants will be analyzed according to the treatment they received.

**PK Set:** All participants in the SAF and for whom at least 1 post dose serum PK concentration is available, excluding placebo participants.

**PD Set:** All participants in the SAF for whom at least 1 post-baseline value for PD parameter (including free C2, total C2 and CH50) is available

The SAF set will be used to analyze the primary safety analysis. The SAF will be used to analyze efficacy endpoints.

For analyses performed on the SAF, PK and PD sets, the actual treatment arm will be considered.

[REDACTED]

If a treatment switch or misallocation occurred, sensitivity analyses might be performed.

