## 9.2 List of Tables, Figures and Listings

### 9.2.1 Tables and Figures

**Table 24 List of Tables and Figures**

TABLE/ FIGURE	NUMBER	TITLE	Interim Analysis 1 (cohort 1)	Interim Analysis 2 (cohort 1 + cohort 2)	Final analysis (cohort 1 + cohort 2)
GENERAL CHARACTERISTICS					
Table	14.1.1	Overall Disposition - Enrolled Set	x	x	x
Table	14.1.2	Overall Disposition - Safety Set	x	x	x
Table	14.1.3	Participants Disposition - by Country and Site - Enrolled Set	x	x	x
Table	14.1.4	Participants Disposition by Country and Site - Safety Set	x	x	x
Table	14.1.5	Study Periods Duration - Safety Analysis Set	x	x	x
Table	14.1.6	Protocol Deviations - Safety Set		x	x
Table	14.1.7	Overview of Analysis Sets - Enrolled Set	x	x	x

Table	14.1.8	Demographic and Baseline Characteristics - Safety Set	x	x	x
Table	14.1.9	Medical History - Safety Set		x	x
Table	14.1.10	MMN Disease History - Safety Set	x	x	x
Table	14.1.11	Confirmation of Diagnosis and IVIg Dependency by MCC - Safety Set	x	x	x
Table	14.1.12	IVIg History - Safety Set	x	x	x
Table	14.1.13	IVIg Treatment during IVMP - Safety Set	x	x	x
Table	14.1.14	Prior Medications - Safety Set		x	x
Table	14.1.15	Prior Procedures - Safety Set		x	x
Table	14.1.16	Summary of concomitant medications during DBTP - Safety Set		x	x
Table	14.1.17	Summary of concomitant procedures during DBTP - Safety Set		x	x
Table	14.1.18	IMP Exposure and Compliance - Safety Set		x	x
Table	14.1.19	Summary of DBTP Baseline Scores for Efficacy Endpoints		x	x
EFFICACY					
Table	14.2.1.1	Time to First Retreatment with IVIg during DBTP [1] - Safety Set	x	x	x

Figure	14.2.1.2	Time to First Retreatment with IVIg - Safety Set	x	x	x
Table	14.2.1.3	Time to Relapse during DBTP - Safety Set	x	x	x
Figure	14.2.1.4	Time to Relapse during DBTP - Safety Set	x	x	x
Table	14.2.1.5	Retreatment with IVIg during the DBTP - Safety Set	x	x	x
Table	14.2.1.6	Retreatment with IVIg Status according to Worsening status during DBTP - Safety Set	x	x	x
Table	14.2.1.7	Retreatment with IVIg Status according to Worsening status during DBTP - Safety Set	x	x	x
Table	14.2.1.8	Summary of mMRC-10 Sum Score during IVMP and DBTP - Safety Set	x	x	x
Table	14.2.1.9	Summary of mMRC-10 Sum Score during IVMP and DBTP by IVIg Dose Frequency Subgroup - Safety Set	x	x	x
Table	14.2.1.10	mMRC-10 Sum Score during DBTP - Analysis of Covariance - Trial-product strategy [1] - Safety Set	x	x	x

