9.2.2 Listings

**Table 25** List of Listings

	NUMBER	TITLE	Interim Analysis 1 (cohort 1)	Interim Analysis 2 (cohort 1 + cohort 2)	Final analysis (cohort 1 + cohort 2)
TREATMENT ALLOCATION					
Listing	16.1.7.1	Allocation Treatment and IVIg Dose Frequency Stratification Factor - Safety Set	x		x
DISPOSITION					
Listing	16.2.1.2	Participant Disposition and Study Termination - Safety Set	x		x
Listing	16.2.1.4	Analysis Sets - Enrolled Set	x		x
PROTOCOL DEVIATIONS					
Listing	16.2.2.1	Protocol Deviation - Safety Set	x		x
Listing	16.2.2.2	Inclusion Criteria Not Met - Enrolled Set	x		x
Listing	16.2.2.3	Exclusion Criteria Met - Enrolled Set	x		x
PARTICIPANTS EXCLUDED FROM THE EFFICACY ANALYSIS					
Listing	16.2.3.1	Non randomized Participants (ENR minus SAF)			x
DEMOGRAPHICS					
Listing	16.2.4.1	Demographic and Baseline Information - Safety Set	x		x
Listing	16.2.4.2	Medical History - Safety Set	x		x

Listing	16.2.4.3	MMN disease history - Safety Set	x		x
Listing	16.2.4.4	IVIg history - Safety Set	x		x
Listing	16.2.4.5	IVIg treatment during IVDP and IVMP - Safety Set	x		x
Listing	16.2.4.6	Prior Medications - Safety Set	x		x
Listing	16.2.4.7	Prior Procedures - Safety Set	x		x
Listing	16.2.4.8	Concomitant Medications - Safety Set	x		x
Listing	16.2.4.9	Concomitant Procedures - Safety Set	x		x
EXPOSURE AND COMPLIANCE					
Listing	16.2.5.1	Detailed IMP Exposure by Visit - Safety Set	x		x
Listing	16.2.5.2	Overall IMP Exposure by Participant during DBTP - Safety Set	x		x
EFFICACY					
Listing	16.2.6.1.1	Time to Retreatment with IVIg - Safety Set	x		x
Listing	16.2.6.1.2	Time to relapse - Safety Set	x		x
Listing	16.2.6.1.3	Detailed IVIg Exposure during DBTP - Safety Set	x		x
Listing	16.2.6.1.4	Overall IVIg Exposure during DBTP - Safety Set	x		x
Listing	16.2.6.1.5	mMRC-10 and mMRC-14 Sum Scores assessments - Safety Set	x		x
Listing	16.2.6.1.6	GS Daily Average assessments at Visits - Safety Set	x		x
Listing	16.2.6.1.7	GS 3 Day Moving Average - Safety Set	x		x
Listing	16.2.6.1.8	MMN-RODS assessments - Safety Set	x		x
Listing	16.2.6.1.9	9-HPT assessments - Safety Set	x		x

Listing	16.2.6.1.10	EQ-5D-5L assessments - Safety Set	x		x
Listing	16.2.6.1.11	CAP-PRI assessments - Safety Set	x		x
Listing	16.2.6.1.12	PGIC assessments - Safety Set	x		x
Listing	16.2.6.1.13	FSS assessments - Safety Set	x		x
Listing	16.2.6.1.14	HRPQ assessments - Safety Set	x		x
Listing	16.2.6.1.15	TSQM-14 assessments - Safety Set	x		x

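### The count of participants randomised but not dosed is taken within the Safety Set, where it can only be zero, and Listing 16.2.3.1 carries a title that is wrong for any such participant

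*SAP*

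**What the plan says.** Section 4.1 of the SAP defines the Safety Set (SAF) as "All enrolled participants who were randomized and received at least 1 dose, or part thereof, of IMP (ARGX-117 or placebo"). The Enrolled Set (ENR) is wider: "all participants who signed an informed consent to participate to the trial". Efficacy as well as safety is analysed on the SAF.

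Section 6.3.1 plans two disposition tables. The one for enrolled participants includes the number randomised but has no row for those not dosed. The other is introduced as follows: "A tabulation of participant disposition will be presented for each cohort by treatment group and overall, for SAF set, including". Its rows include the number randomised and "Number of participants randomized but not dosed". Table 24 lists it as Table 14.1.2, "Overall Disposition - Safety Set".

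In Table 25 (section 9.2.2), the only listing under the heading for participants excluded from the efficacy analysis is 16.2.3.1, titled "Non randomized Participants (ENR minus SAF"). It is planned for the final analysis only. Listings 16.1.7.1 (treatment allocation) and 16.2.1.2 (disposition and study termination) are both on the Safety Set.

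On the analysis-set counts, section 6.3.1 says: "The number of participants in each analysis set will be also presented in the SAF set". Table 24 gives the matching output, Table 14.1.7, the title "Overview of Analysis Sets - Enrolled Set".

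**The concern.** The sponsor meant to report participants who were randomised and never received study drug, since a row was written for them. That row sits on a population from which they are excluded by definition. The one listing that would contain them describes them as something they are not.

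Because efficacy is analysed on the SAF, these participants are the post-randomisation exclusions from every comparison between arms. A reader judging the randomised comparison wants their number, arm and reason. The planned table would state 0, and the planned listing title would say that nobody in it was randomised.

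**Working it through.** The plan gives no figure to reproduce. The check is set logic on its own definitions.

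**Definitions.** Let R be randomised and D be dosed, in whole or in part. From section 4.1, SAF = R and D. ENR is everyone who consented.

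**Row in the SAF table.** The count wanted is (R and not D). Within SAF this is (R and D) and (R and not D), which is empty, so the row is 0 for any data. The number randomised within SAF is R and (R and D) = SAF, so that row always equals the SAF size.

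**Listing 16.2.3.1.** ENR minus SAF = (not R) plus (R and not D). This equals the non-randomised group only when (R and not D) is empty. Otherwise the title is false for each member of that second part.

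**Illustration.** The SAP gives no number for those randomised but not dosed, so k below is assumed. The 48 is the planned number randomised in section 6.1.

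| k (assumed) | SAF table: randomised (48 − k) | SAF table: randomised but not dosed | ENR table: randomised | Randomised people listed as non-randomised |
|---|---|---|---|---|
| 0 | 48 | 0 | 48 | 0 |
| 1 | 47 | 0 | 48 | 1 |
| 2 | 46 | 0 | 48 | 2 |
| 3 | 45 | 0 | 48 | 3 |

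**What one participant would mean for an arm.** If a cohort randomises exactly 24 at 2:1, the arms are 24 × 2/3 = 16 and 24 × 1/3 = 8. One participant is then 1/16 = 6.3% of the active arm or 1/8 = 12.5% of placebo. These are illustrations only. Section 2.1 says at least 24 per cohort, and section 2.2 gives 2:2:1:1 for option 3 in cohort 2.

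**Can other outputs supply the answer?**
- *Total:* yes. The number randomised in the ENR table minus the SAF size gives k (in the table above, 48 − 47 = 1 when k = 1). Listing 16.2.1.4 is also on the Enrolled Set.
- *Split by arm:* unclear. Section 6.3.1 first says that ENR summaries are presented overall. Its next paragraph says that the enrolled disposition table is by treatment group and overall. Only under the second statement can the subtraction be done by arm.
- *Arm and reason for the individual:* not in Listings 16.1.7.1 or 16.2.1.2, which are restricted to the Safety Set.

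**The case against.** The strongest reply is that little is lost. Randomisation and first dose are both planned for day 1, so the number affected may well be 0. The total follows from one subtraction. Listing 16.2.3.1 states its rule beside its title, and the rule fits the heading it sits under, so the participants do appear there. No estimate, interval or safety rate changes. All of this stands, and it is why the point is minor.

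Several stronger readings are tempting, but the SAP does not support them:

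- *The arm of such a participant is reported nowhere.* A reader could infer this from the sentence saying that ENR data are presented overall. The next paragraph of section 6.3.1 says by treatment group and overall. The text contradicts itself, and the loss of arm information is possible but not established.
- *The outputs turn these people into screen failures.* Section 6.3.1 defines screen failures as those who consented but were not then randomised, so no table counts them that way. Only a listing title is wrong.
- *Failing eligibility at V1 makes the case likely.* The sentence on V1 describes screen failures, who by definition were not randomised. Something would have to happen between randomisation and infusion.

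What the reply does not remove is that a planned row states 0 by construction. A reader should not have to subtract across two tables to find that it carries no information.

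**Conclusion.** The point holds as a disposition-reporting defect. The row for participants randomised but not dosed is 0 by definition, the row for the number randomised in the same table is the SAF size by definition, and the title of Listing 16.2.3.1 is false for anyone randomised and never dosed. This follows from sections 4.1, 6.3.1 and 9.2 alone.

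The misstatement equals the true number randomised but not dosed, which the SAP does not give and which may be 0. The total is recoverable indirectly. Recovery by arm depends on which of two conflicting sentences in section 6.3.1 governs. A reader might infer that the efficacy results are affected. They are not changed by this defect, because the choice of the SAF for efficacy is a separate matter and correcting the row and title leaves every estimate as it is. Severity: minor reporting correction.

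**What to change.** 1. Move the rows for randomised and for randomised but not dosed to the Enrolled (or an all-randomised) disposition table, by cohort and randomised arm. State once in section 6.3.1 whether that table is shown by arm, and remove the conflicting sentence.
2. Keep ENR minus SAF as the rule for Listing 16.2.3.1, since it matches the heading on exclusions from efficacy. Retitle it *Participants not in the Safety Set*, and add a flag for not randomised versus randomised but not dosed, with the arm and the reason. Redefining it as enrolled minus randomised would drop the very participants at issue and call for a second listing.
3. Change the sentence in section 6.3.1 on analysis-set counts so that it refers to the Enrolled Set, as the title of Table 14.1.7 already does.

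The cost is SAP wording, one moved block of rows and one flag. No new data are needed and no analysis changes.

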### 6.3.2 Demographic and Baseline Characteristics

Baseline, demographic, medical history, MMN disease history, IVIg history, will be summarized using descriptive statistics. Summary data for the SAF set will be presented for each cohort by treatment group and overall.

#### 6.3.2.1 Demographics

Demographics will be summarized for the SAF sets.

CRS-BS-TP-000005 V 2.0

Demographics and baseline data include age (years), sex, ethnicity, race, height (cm), weight (kg) and BMI (kg/m^2). All data are collected at screening visit only except weight that is collected at screening and IMV3. BMI is auto calculated, defined as: Weight (kg)/(Height\*Height) (m^2).

Frequency tabulations will be provided for age category, sex, race, ethnicity, and region. Subgroup categories are defined in section 6.2.6.2. For race and ethnicity categories are per eCRF categories will be presented.

Demographic and baseline data will be provided in data listings.

#### 6.3.2.2 Medical history

Medical history will be summarized for the SAF set.

Medical history (resolved and ongoing at screening) is summarized by participant incidence rates; therefore, a participant contributes only once to the count for a given medical history (SOC or preferred term).

Medical history will be reported in a listing.

#### 6.3.2.3 MMN disease history and MMN diagnosis

MMN disease history will be summarized for the SAF set.

Estimated duration of the disease since diagnosis at randomization will be derived as follows:

Estimated duration of disease since diagnosis = (Date of randomization – date of diagnosis +1)/365.25.

For the date of diagnosis:

- if day and month are missing, 01-Jul will be imputed
- if day is missing, 15 will be imputed.

Estimated duration of the disease since diagnosis at randomization, the most affected hand and the 2 most important muscles groups affected by MMN will be reported.

For the estimated duration of the disease since diagnosis at randomization in the summary table, results will be rounded in year with no decimal places for min and max, one decimal place for mean median and 2 decimal places for SD.

A tabulation will summarize the confirmation of diagnosis and IVIg dependency at screening and IMV1 in the SAF set.

MMN history will be reported in a listing. Confirmation of diagnosis and IVIg dependency by MCC will be listed.

